Sleep breathing disorders which includes obstructive sleep apnea (OSA) snoring, has an estimated prevalence of 3 - 7% of the adult US population. OSA subjects experiencing chronic sleep debt and intermittent nocturnal hypoxia are more prone to health risks that includes carbohydrate metabolism imbalance, immune and endocrine dysfunction (Table 1).² Continuous positive airway pressure (CPAP) is the American Academy of Sleep Medicine (AASM) treatment recommendation for this highly prevalent disorder. However, approximately 30% of OSA patients do not tolerate CPAP.4

Alternative treatment options for OSA include surgical interventions, mandibular advancement splint also referred to as oral appliance (OA) therapy, tongue retaining and hypoglossal nerve stimulating devices, but these have debatable efficacy in moderate and severe OSA. Efficacy differences in OA therapies treatment of moderate and severe OSA could be related to OA design variations although this hypothesis has not been tested. Hoekema et al. (2007b) used a custom-fitted midline traction (MT) OA and found large improvements in Epworth Sleepiness Scale (ESS) scores, oxygen saturation levels, Quality of Life, Short Form (SF)-36 scores and the apnea hypopnea index (AHI) in a randomized control trial (RCT) in severe OSA subjects. ⁵ Three other RCT studies from

Hoekema (2007a, 2008a, 2008b) and two other reports also used the same MT-device in moderate and severe OSA patients. ⁶⁻¹⁰ AHI improvements ranged from 80 to 90% (mean 85%). In contrast, several studies in moderate and severe OSA patients using bilateral thrust (BT) design failed to demonstrate an AHI reduction <10 events/hour although showing >50% AHI reduction (mean 55.4%; range 53 – 57%) from baseline conditions. ¹³⁻¹⁹ Of the OA studies considered in the American Academy of Dental Sleep Medicine (AADSM) practice guidelines, four (67%) used a MT OA, compared with only one (14%) in seven studies that used BT OA in severe OSA subjects (Table 2).²⁰ The mean pre-OA AHI was 40.1 events/hour that reduced to a mean 5.7 events/hour post-treatment in the MT OA reports. The single BT OA study in severe subjects had a pre-treatment AHI equal to 30 events/hour that reduced to 14 events/hour at post-OA treatment.

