Purpose: The two prominent OAs used in treating obstructive sleep apnea (OSA) differ in their designs, MT versus BT. From a clinical perspective, it is important to know which design is superior and should be the 'treatment of choice' for improving airway function and sleep quality. These two designs differ in their protrusive mechanisms that are categorized in general under four main types: bilateral compression, bilateral traction, midline compression and midline traction. Although the two designs considered in this proposal have undergone the most rigorous testing individually, well controlled 'head-to-head' trials as proposed here have not been conducted to determine their efficacy within a single test population.

Patients/Methods: Adults (n=44) with moderate to severe OSA diagnosed by polysomnography (PSG) or home sleep test (HST) within the previous year, who are using CPAP therapy, will be recruited and selected to enter the study. The study duration will be approximately nine months and each patient is expected to participate in the study for nine consecutive weeks. The first 4-weeks involve using one of either MT or BT OAs followed by 1-week washout period, then 4-weeks using the second OA. Home sleep recordings will be collected at T_1 -first OA start; T_2 -end first OA; T_3 -second OA start; T_4 -end second OA. The primary outcome measure will be the respiratory disturbance index (RDI).

Table 1: Examples of sequela associated with OSA in adults.

Health Consequences	Adult
Excessive daytime sleepiness	√
Reduced Quality of Life	√
Accidents (i.e. occupational, motor vehicular)	√
Hypertension	\checkmark
Cardiovascular disease	√
Obesity	√
Neuromuscular disorders	\checkmark
Sleep quality	√
ADHD	\checkmark
Learning difficulty; Cognitive impairment; Dementia; Alzheimer's	√
Disease	
Behavior problems	\checkmark
Sleep-walking	\checkmark
Hormonal & metabolic problems	\checkmark
Bruxism	√
Depression	√
Impotence	√

Table 2: Select oral appliance studies using midline traction and bilateral thrust

	al appliance studies using iniu					
			pre			%
Device	Study	post AHI	AHI	#pts		improvement
TAP -MT	Hoekema2007a	3.2	20.4	20	Moderate	84%
TAP - MT	Hoekema2007b	5.2	50	9	Severe	90%
TAP - MT	Hoekema2008a	4	31	12	Severe	87%
TAP - MT	Hoekema2008b	7.8	39.4	51	Severe	80%

TAP - MT	Holley 2011*	8.4	30	497	Severe	72%
TAP - MT	Ghazal 2009	7.9	22.2	48	Moderate	64%
Somnodent - BT	Deane 2009	12	27	22	Moderate	56%
Somnodent - BT	Gotsopoulos 2002	12	27	73	Moderate	56%

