An increase in oropharyngeal space created by advancement of the mandible occurs in association with inferior movement of the condyles that causes the posterior aspect of the mandible to move away from the maxilla (Christensen's phenomenon). ²¹ The mandible's forward movement away from the maxilla stretches and tightens the lateral walls of the pharynx with the superior constrictor muscle through attachments that includes the tongue. ²¹ Furthermore, this space creating forward movement allows the tongue to rest behind the upper incisors to form an air seal with the soft and hard palate that then facilitates nose breathing. ²¹ An OA's mechanics to move the mandible forward should increase oropharyngeal space with concomitant reduction in the number of apnea and hypopnea events through increased forward torque on the lumen's surrounding musculature.

Midline Traction OA	Bilateral Thrust OA

Provides customized fit for each patient	√	√
Uses separate upper and lower tray pieces	V	√
Advances mandible incrementally	√	√
Advancements performed by a dental sleep specialist	√	√
Single contact point between upper and lower trays	V	
Pulls mandible forward	√	
Two contact points between upper and lower trays		√
Pushes mandible forward		√

V.Hypothesis

 $\rm H_0$: The RDI will not differ when treating adults with moderate to severe (>15 events/hour) OSA between the MT and BT devices. $\rm H_A$: The MT device / intervention will provide greater reduction in the RDI from pretreatment values than the BT device in adults with moderate to severe OSA. Secondarily, proportions of responders to MT device intervention who's RDI is reduced to an acceptable level (< 10 events/hour or >50% change from pre-treatment values) is expected to be higher with MT therapy.

VI.Objectives

The main study objectives are to:

- 1. Quantify the RDI with each OA at the start and end of four weeks of use.
- 2. Compare the RDI of each OA with pre-treatment PSG determined AHI to evaluate the percent reduction.
- 3. Characterize global sleep quality changes associated with the use of the OAs.

We endeavor to model real-world conditions for measuring sleep by utilizing HST and recording in the subject's own sleep environment. Based on previous research, we expect reduction in the RDI with OA use and superior response with the MT OA.

VII.Methods

- a. Study type
 - 1. Single center, cross-over randomized control trial; superiority trial

2. Interventional comparative effectiveness research

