Treatment devices: TAP 1 (Airway Management Inc., Dallas, TX; MT type OA device) and SomnoDent Flex (SomnoMed, Plano, TX; BT type OA). Both OA devices will be used per manufacturers' recommendations. To insure comparability, both devices have a custom thermal acrylic liner insuring a very accurate fit. Each subject will also be custom fitted with a mandibular positioner ("AM Aligner" or "Morning Positioner") to use for up to 20 minutes after awakening in the morning; this will assist in returning the subject to his/her normal occlusion.

Appliance Acclimation: Both appliances will be adjusted / titrated to the patient's maximal comfortable protrusive position by patient in the wake state. The starting position will be determined by the patient at a comfortable position but not less than 60% as determined by the Pro Gauge. "Comfortable" is defined as the advanced mandibular position that permits the subject to sleep for ≥ 5 hours per night for at least 6 nights of the week. Subjects will use diaries to record appliance settings and hours of sleep on each sleep recorded or non-recorded night. Two follow-up nights (post T_1) of SleepImage recordings only will be made to track sleep quality and OA position, if further mandibular adjustments are necessary as determined by the T_1 & T_3 HST and SleepImage results.

Course of Treatment: Subjects will be randomly assigned to either the MT- or BT-first OA device as treatment for OSA. Each subject will use the first OA for 4 weeks followed by – 1 week washout period that includes using nightly their prescribed CPAP and daytime use of a mandibular positioner (for up to 20 minutes) – then another 4 weeks of active treatment with the second OA.

h. Power Analysis and Sample Size

At least 38 subjects with OSA are needed to yield a power of 0.90 with alpha = .05 and an expected Effect Size of at least a 10 point difference in the post-treatment mean RDI scores between MT vs. BT devices.Recruitment will be extended to n=44 to accommodate an estimated 20% drop-out rate. The projected numbers are based on Wilcoxon signed-rank test where the expected difference between-treatments (cross-over design) is expected to be at least 10 point difference in RDI scores.

i. Statistical analyses

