13.0 Study Population
13.1 Number of Participants
Approximately how many subjects do you plan to enroll?
38
Provide the rationale for the number of subjects requested (for example, power analysis, sponsor requirements, etc.).
Approximately 38 subjects must complete the study to yield a power of 0.90 with alpha = .05 and an expected Effect Size of at least a 10 point difference in the post-treatment mean RDI scores between MT vs. BT devices. Recruitment will be extended to n=44 to accommodate a 10-20% drop-out rate. The projected numbers are based on Wilcoxon signed-rank test where the expected difference between-treatments (cross-over design) is expected to be at least a 10 point difference in RDI scores. As many as 44 will be enrolled to account for attrition.
Will human subjects be used from the Qatar population?
○ Yes • No
* If Yes, then approval by an IRB in Qatar may also be required.
Will human subjects be used from another international population?
C Yes O No
*If Yes, then approval by an international review board or government may also be required.
Will human subjects be used from a Native American population?
O Yes ⊙ No
*If Yes, then approval by a tribal IRB(s) may also be required.
If Yes for research in Qatar, in another country, or with Native Americans, provide justification for that research being conducted in that particular community.
13.2 Provide the age groups being enrolled into this study (Note the consent documents required for each age group listed in parentheses):
 □ 0-6 (parental consent only, Pediatric Assessment required for Clinical Trials) □ 7-11 (child's assent plus parental permission, Pediatric Assessment required for Clinical Trials) □ 12-17 (consent plus parental permission, Pediatric Assessment required for Clinical Trials) ▼ 18+ (consent only)
Enter the specific age range for study population (if overlap or specific within a category):

13.3 Indicate the gender of participants being enrolled into this study:	
MaleFemale✓ Both male and female	

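### Is the 90% power claim undermined because the 10-point RDI difference comes with no SD, sidedness or source, and exceeds the raw contrasts in the plan's own evidence?

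*Combined protocol and SAP*

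**What the plan says.** Section VII.h bases 38 completers, at power 0.90 and alpha .05 with a Wilcoxon signed-rank test, on an "expected Effect Size of at least a 10 point difference in the post-treatment mean RDI scores between MT vs. BT devices". Section 13.1 repeats this: the between-device difference "is expected to be at least a 10 point difference in RDI scores". Neither place gives an SD of paired differences, says whether the test is one- or two-sided, or shows where the 10 comes from.

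Section V pairs a null hypothesis of no difference with a directional alternative, that MT "will provide greater reduction in the RDI from pretreatment values than the BT device".

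The evidence is in section I (Background and Significance) and Table 2. For severe disease, section I reports: "The mean pre-OA AHI was 40.1 events/hour that reduced to a mean 5.7 events/hour post-treatment in the MT OA reports". For BT it reports: "The single BT OA study in severe subjects had a pre-treatment AHI equal to 30 events/hour that reduced to 14 events/hour at post-OA treatment". Table 2 lists six MT and seven BT studies with AHI before and after treatment.

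**The concern.** The plan calls 10 points expected, not a minimum important difference, so it is fair to compare it with the plan's own evidence. On the post-treatment scale that the power sentence uses, every summary of that evidence falls short: 3.9, 6.1 or 8.3. With no SD, the 38 cannot be recalculated forwards either.

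If the true difference were about 6 points and the SD the one that 38 pairs imply, power would be near one half rather than 0.90. A null result in a superiority trial would then say little.

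**Working it through.** **1. The plan's 38.** It cannot be reproduced forwards without an SD, so solve for the SD instead. For the signed-rank test under normality, use an effective n of 38 × 3/π = 36.3 in the paired noncentral t. Power 0.90 then needs difference/SD = 0.553 two-sided or 0.495 one-sided.
- Two-sided: SD = 10/0.5534 = 18.1.
- One-sided: SD = 10/0.4954 = 20.2.

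The plain normal formula agrees closely: two-sided, SD = 10 × √36.3 / (1.960 + 1.282) = 18.6. Simulating the signed-rank test itself (6,000 runs, n = 38, SD 18.1, two-sided) gives 0.90 at 10 points.

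**2. Raw post-treatment contrasts (BT minus MT).**
- Table 2, unweighted: 85.3/7 − 36.5/6 = 12.19 − 6.08 = 6.1.
- Table 2, weighted by patients: 11.90 − 8.02 = 3.9. One MT row holds 497 of the 637 MT patients; without it the difference is 11.90 − 6.68 = 5.2.
- Section I, severe reports: 14 − 5.7 = 8.3.

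**3. The scale of the hypothesis.** In this crossover each patient has one pre-treatment value B. The between-device difference in reduction is (B − MT) − (B − BT) = BT − MT, which is the post-treatment difference. Within the trial the two scales are the same. Across separate studies they are not, because the baselines differ.

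| Source | MT baseline | BT baseline | Raw gap | Gap in reduction |
|---|---|---|---|---|
| Table 2, unweighted | 32.2 | 27.2 | 6.1 | 26.08 − 15.01 = 11.1 |
| Table 2, weighted | 30.2 | 26.8 | 3.9 | 22.14 − 14.86 = 7.3 |
| Section I, severe | 40.1 | 30 | 8.3 | 34.4 − 16 = 18.4 |

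**4. A common baseline.** The raw gap tends to understate an MT advantage, because MT patients started higher. The gap in absolute reduction can overstate it, because a higher start leaves more room to fall. Percent reductions applied to one baseline are a compromise.
- Section I's 85% v 55.4% gives 0.296 × baseline: 8.7 at 29.5 (the mean of the 13 Table 2 baselines), 11.9 at 40.1, and 10 at 33.8.
- Section I's severe figures, 85.8% v 53.3%, give 9.7 at 30, 13.0 at 40.1, and 10 at 30.8.
- All Table 2 rows, 79.6% v 55.2%, give 7.2 at 29.5, 9.8 at 40.1, and 10 at 41.0.

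Ten lies inside the range of these results, towards the favourable end for a baseline near 30.

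**5. What 38 completers deliver.** Two-sided power. Every SD except 18.1 is an assumption that the documents do not give.

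| SD of paired differences | 10 points | 8.3 | 6.1 | 3.9 | Pairs for 0.90 at 10 points |
|---|---|---|---|---|---|
| 10 | >0.99 | >0.99 | 0.95 | 0.63 | 14 |
| 12 | >0.99 | 0.98 | 0.85 | 0.48 | 18 |
| 15 | 0.97 | 0.90 | 0.66 | 0.33 | 27 |
| 18.1 (implied) | 0.90 | 0.77 | 0.51 | 0.24 | 38, by construction |
| 20 | 0.83 | 0.68 | 0.43 | 0.21 | 47 |
| 25 | 0.65 | 0.49 | 0.30 | 0.15 | 71 |

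**The case for a change.** The strongest case for a change is that this is the only rationale printed for the sample size and it cannot be checked. The routes to 10 are favourable ones. The 85% in section I matches four of the six MT rows; the other two (72% and 64%) hold 545 of the 637 MT patients. Only 2 of the 13 Table 2 rows, with 60 of 1,065 patients, start at or above 33.8. Entry needs only an AHI above 15, and no expected mean baseline is stated. If the SD actually used was 12 or 15, then 38 does not follow from 10 points, because 18 or 27 pairs would do.

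Most of this stands as description. The SD, sidedness and basis are missing, and a sentence giving them would have been good practice. Three things limit what follows.
- The evidence is AHI from separate studies, whereas the endpoint is RDI per recorded hour from home testing. It cannot settle whether 10 is right or wrong.
- An SD below 18 would make the trial better powered than claimed, not worse. Only a larger SD hurts, and nothing in the documents points to one.
- Every remedy on offer keeps the 38 and the signed-rank test. It would add values the sponsor presumably already had, or a power table at SDs chosen by the reader.

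Whether 44 recruits cover 20% drop-out (44 × 0.8 = 35.2, giving power of about 0.87 at the implied SD) is a separate question from the basis of the 10 points.

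**Conclusion.** No change follows. This is missing documentation, not an error: nothing is miscalculated, and the 90% is unsupported on the page rather than shown to be false. The plan's evidence runs from 3.9 to 8.3 points on raw post-treatment means and from 7.3 to 18.4 on reduction from baseline, so an expected 10 is optimistic on some readings and modest on others.

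An analyst can fill the gap sensibly. The null of no difference supports a two-sided reading, and the stated inputs then fix the planning SD at about 18 (about 20 if one-sided). Once the trial has run, the observed SD of paired differences and the interval around the device difference show what a null result can exclude, and planned power no longer matters for that.

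The conclusion rests on roughly normal paired differences, 38 completers, and cross-study AHI as a rough guide to RDI. Its weak side is an SD above 18: two-sided power at 10 points would be 0.83 at SD 20 and 0.65 at SD 25.

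### Recruiting 44 does not cover the stated 20% drop-out: about 35 subjects would complete, not the 38 on which the 0.90 power rests

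*Combined protocol and SAP*

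**What the plan says.** The sample size is described in two places.

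- **Section VII.h (Power Analysis and Sample Size):** "At least 38 subjects with OSA are needed to yield a power of 0.90 with alpha = .05", for a difference of at least 10 RDI points between the devices, based on a Wilcoxon signed-rank test. It continues: "Recruitment will be extended to n=44 to accommodate an estimated 20% drop-out rate".
- **Section 13.1 (Number of Participants):** "Approximately 38 subjects must complete the study to yield a power of 0.90 with alpha = .05", followed by "Recruitment will be extended to n=44 to accommodate a 10-20% drop-out rate" and a statement that enrolment may reach 44 to allow for attrition. In the same section, the form question "Approximately how many subjects do you plan to enroll" is answered with 38.

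The abstract (Patients/Methods) and section VII.b (Population) both give n=44. Section VII.i (Statistical analyses) names the matched-pairs Wilcoxon signed-rank test for the primary variables. No SD of the paired differences, sidedness or formula for the drop-out allowance is given.

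**The concern.** Section VII.h reads as an assurance that 0.90 power survives a 20% drop-out. Because 38 is a count of completers, 44 recruits would have to leave 38 after 20% are lost, and they do not. The completers required, the drop-out rate and the recruitment target cannot all hold.

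The primary test is paired, so each subject must supply a value on both appliances. A subject lost before T4 has no observed end-of-treatment pair. Participation runs for nine weeks, with two appliances and a washout, so attrition is a real planning quantity here.

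The two sections also disagree on the rate (20% against 10–20%), and the enrolment entry of 38 contradicts the text beneath it. A reader cannot tell which enrolment and attrition figures the power statement assumes.

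**Working it through.** **Inputs**

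| Quantity | Value | Source |
|---|---|---|
| Completers required | 38 | VII.h; 13.1 (must complete) |
| Power, alpha | 0.90, 0.05 | VII.h; 13.1 |
| Recruitment target | 44 | VII.h; 13.1 |
| Drop-out | 20%; 10–20% | VII.h; 13.1 |
| Sidedness | not stated; the alternative in section V is directional | both computed |
| SD of paired differences | not stated | not needed below |

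**1. Trying to reproduce 44**

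The allowance for a drop-out proportion d is N/(1 − d).

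- d = 0.20: 38/0.80 = 47.5, so 48.
- The common but incorrect form N × (1 + d): 38 × 1.20 = 45.6, so 46.
- d = 0.10: 38/0.90 = 42.2, so 43.

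Neither form gives 44 at 20%. The incorrect form does give 44 at 15% (38 × 1.15 = 43.7).

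**2. What 44 delivers**

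Largest attrition that keeps 38 completers: 1 − 38/44 = 6/44 = 13.6%.

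| Drop-out | Completers, 44 × (1 − d) | At least 38? |
|---|---|---|
| 10% | 39.6 | yes |
| 13.6% | 38.0 | just |
| 15% | 37.4 | no |
| 20% | 35.2 | no |

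These are expected counts. If each of 44 subjects independently has a 0.80 chance of completing, the binomial probability that 38 or more complete is about 0.20. With a 0.90 chance of completing it is about 0.85.

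**3. Power at the reduced number**

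Take the plan's statement that 38 pairs give 0.90 as the calibration point. The unstated SD and the efficiency of the Wilcoxon test then cancel:

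power(n) = Φ[(z_α + z_0.90) × √(n/38) − z_α]

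- Two-sided, n = 35: (1.960 + 1.282) × √(35/38) − 1.960 = 3.242 × 0.960 − 1.960 ≈ 1.151, and Φ(1.151) = 0.875.
- One-sided, n = 35: (1.645 + 1.282) × 0.960 − 1.645 ≈ 1.164, and Φ(1.164) = 0.878.

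Checks at n = 35, each with the effect set to give about 0.90 at 38:

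- Paired t test (noncentral t): 0.874 two-sided, 0.877 one-sided.
- Simulated two-sided Wilcoxon signed-rank test on normal differences, standardised effect 0.55: 0.902 at n = 38 and 0.872 at n = 35.

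**4. If the enrolment entry of 38 were taken literally**

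38 × 0.80 = 30.4, so about 30 pairs. Power is then about 0.815 two-sided or 0.827 one-sided (noncentral t with Wilcoxon efficiency 0.955). This applies only under that reading of the form field.

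**The case against.** Five points can be made for the plan.

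- **The range.** Section 13.1 says 10–20%, and 44 is enough at the lower end. That is true up to 13.6%. But the range includes 20%, and section VII.h gives 20% alone, so the claim as written there still fails.
- **Imputation.** Section VII.i lists last observation carried forward, multiple imputation and mean imputation for the primary endpoint. A subject lost between T3 and T4 has a first-night RDI on the second appliance and could enter an imputed analysis, so such a subject is not wholly without a pair. However, the plan labels this set a sensitivity analysis, imputation does not restore the lost information, and section 13.1 defines the requirement by completion.
- **The size of the loss.** About 2.5 points is small, 35 pairs stay well above 0.80, and the 10-point difference is described as a minimum. This stands, and it limits the weight of the point.
- **The enrolment entry of 38.** The lines below it and three other places say 44, so it is probably clerical. This also stands: the 30-pair figure shows why the entry should be corrected, not what the trial intends.
- **The unverifiable base.** Without an SD, 0.90 at 38 cannot be confirmed. That is a separate and possibly larger uncertainty. It does not rescue 44, because the shortfall in completers follows from the plan's own counts.

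**Conclusion.** The concern holds. At the 20% drop-out in section VII.h, 44 recruits leave about 35 completers, about 3 short of 38. The shortfall begins at any attrition above 13.6%. Power at 35 pairs is about 0.87 to 0.88, whether the test is one- or two-sided, against the stated 0.90.

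The completer counts rest only on the plan's own figures. The power figures assume in addition that 38 pairs give 0.90, which the documents do not allow anyone to check. The effect on the trial is modest and does not threaten its ability to detect the planned difference. The sample-size statement is nonetheless wrong as written, and sections VII.h and 13.1 do not agree with each other.

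**What to change.** Make the same statement in sections VII.h and 13.1, for example:

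> The target enrolment is 44. This keeps 38 completers if attrition is no more than 13.6%. With 20% attrition, about 35 subjects would complete and power would be about 0.87.

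Change the planned-enrolment entry in section 13.1 from 38 to 44, and use one drop-out assumption in both sections.

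The cost is two sentences and one form field, plus an acknowledged loss of about 2.5 points of power at 20% attrition. No extra patients are needed.

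If the sponsor wants 0.90 to hold at 20% drop-out, the target is 48 (48 × 0.80 = 38.4), which is four more subjects. If 44 is to be kept with 0.90 claimed, the plan should justify an attrition assumption of at most 13.6%.
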